## **15.22.2 Serious Adverse Event**

All AEs will be assessed as either serious or non-serious. A serious adverse event (SAE) is any event that results in any of the following outcomes:

- Death
- Life-threatening (i.e., if in the view of the Investigator or Sponsor, the event's occurrence placed the subject at risk of death at the time of the event; it does not refer to an event which hypothetically might have caused death if it were more severe).
- Requires inpatient hospitalization or prolongation of existing hospitalization. (Hospitalization for elective surgery for a pre-existing condition or for surgery planned before study entry is not considered an SAE.)
- A persistent or significant disability/incapacity (permanent or substantial disruption of the subject's ability to perform normal life functions). This definition is not intended to include experiences of relatively minor or temporary medical significance.
- Congenital anomaly/birth defect (an AE that occurs in the child or fetus of a subject exposed to study drug prior to conception or during pregnancy).

Important medical event or serious medical condition that does not meet any of the above criteria may be considered an SAE if, based upon appropriate medical judgment, it may jeopardize the subject or may require medical or surgical intervention to prevent one of the outcomes listed above. Examples of such medical events include allergic bronchospasm requiring intensive treatment in an emergency room or at home, blood dyscrasias or convulsions that do not result in inpatient hospitalization, or the development of drug dependency or drug abuse.

## 15.22.3 AE Severity

The severity of an AE should be determined by the intensity of the AE and will be assessed using the National Cancer Institute (NCI) Common Terminology Criteria for Adverse Events (CTCAE) Version 4.03 (June 14, 2010) Eye Disorders section.

Grade 1	Mild; asymptomatic or mild symptoms; clinical or diagnostic observations only; intervention not indicated.
Grade 2	Moderate; minimal, local or noninvasive intervention indicated; limiting age- appropriate instrumental ADL*.

## Table 3: CTCAE Grading

Grade 3	Severe or medically significant but not immediately life-threatening; hospitalization or prolongation of hospitalization indicated; disabling; limiting self care ADL**.
Grade 4	Life-threatening consequences; urgent intervention indicated.
Grade 5	Death related to AE.

#### Activities of Daily Living (ADL)

\*Instrumental ADL refer to preparing meals, shopping for groceries or clothes, using the telephone, managing money, etc.

\*\*Self care ADL refer to bathing, dressing and undressing, feeding self, using the toilet, taking medications, and not bedridden

#### **15.22.4 Study Drug Causality**

The Investigator will assess the relationship of the AE to the study drug as either "Related" or "Not Related". The following should be taken into consideration when assessing SAE causality:

- Positive temporal relationship to study drug, such as if the study drug was withdrawn and the AE resolved or the event recurred after re-introduction.
- If there is a reasonable possibility that the AE is associated with an underlying or concomitant illness.
- Possible association with previous or concomitant therapy.
- No temporal relationship to the study drug and/or a more likely alternative etiology exists.
- If the AE is directly related to study procedures or lack of efficacy.

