The administration of single intravitreal doses of ICON-1 was demonstrated to be safe and well tolerated in all three doses tested. There were no systemic or ocular dose-limiting toxicities and a maximum tolerated dose was not determined up to the maximum administered dose of 300  $\mu$ g ICON-1. Most frequently reported adverse events were ocular (conjunctival hemorrhage [n=5], vitreous floaters [n=3], conjunctival edema [n=3], and signs of macular degeneration [n=3]) and commonly related to the injection procedure or the retinal signs of the underlying AMD. Only one adverse event, a case of vitritis in the 300  $\mu$ g cohort was considered by the Investigator to be related to study drug. No retinal or choroidal abnormalities were noted on clinical examination or angiographically. There were no systemic adverse events reported. No significant systemic levels of ICON-1 or antibodies to ICON-1 were detected. Single dose administration of ICON-1 in the Phase 1 study demonstrated preliminary evidence of biologic activity and pharmacodynamic effect relevant to wet AMD; clinical improvement in BCVA, associated with a reduction in CRT (on OCT) and a decrease of CNV area of leakage (on FA) in some patients.

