#### 12.1.2 Test Article Administration

Patients will be enrolled in one of three cohorts:

- 0.3 mg (300  $\mu$ g/100  $\mu$ l) ICON-1 administered on Day 0
- 0.3 mg (300  $\mu$ g/100  $\mu$ l) ICON-1 administered on Day 0 and Day 7
- 0.6 mg (300  $\mu$ g/100  $\mu$ l + 300  $\mu$ g/100  $\mu$ l) ICON-1 administered on Day 0 and Day 7

Using aseptic technique, ICON-1 will be administered by first withdrawing vial contents through a 5-micron 19-gauge filter needle attached to a 1-cc tuberculin or Luer Lock syringe and then replacing the filter needle with a 30-gauge x  $\frac{1}{2}$  inch needle for the intravitreal injection. Adequate topical anesthesia and broad-spectrum microbicide will be given prior to injection.

IOP will be measured before and after each intravitreal injection.

For Cohort 3, the second intravitreal injection will be administered the same day following stabilization of IOP to the pre-injection level (i.e., within 5 mmHg of the pre-injection IOP) and a minimum of 30 minutes after the first injection.

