## 15.22 Evaluation of Adverse Events

Adverse events (AEs) will be monitored continuously during the study from the time that the subject has provided written informed consent through the subject's last day of study participation. AEs may be reported spontaneously by the subject, discovered by Investigator or study staff through questioning, or observed through physical examination or other means. It is the responsibility of the Investigator to assess and document all AEs that occur during the course of the study, regardless of the causal relationship with the study drug.

The following information will be collected for all AEs and recorded on the subject's source document and AE eCRF:

- Event description (diagnosis preferred, if unknown, record the signs/symptoms)
- Onset and resolution dates
- Severity (intensity)
- Frequency (intermittency)
- Relationship to study drug (causality) as determined by the Investigator
- Seriousness
- Action taken with study drug
- Corrective action taken
- Outcome

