#### 17.6 Safety Analyses

Safety will be assessed through summaries of adverse events, changes in laboratory test results (serum chemistry, hematology, coagulation), and changes in vital signs and physical and ophthalmic examinations. Adverse events will be mapped using MedDRA. Systemic levels of

anti-drug antibodies (ADA) during the study will be collected for each patient. If there are sufficient numbers of patients exhibiting systemic levels of ADA, summary statistics by cohort will also be provided.

All collected adverse event data will be listed by cohort, study site, and patient number. All Adverse Events of Special Interest (AESIs) occurring on or after intravitreal injection will be listed and summarized by cohort. All adverse events occurring on or after treatment on Day 0 (treatment emergent adverse events, TEAEs) will be summarized by cohort. In addition, all serious adverse events, including deaths (if any), will be listed separately. Finally, all ocular adverse events will be listed and tabulated with events for the study and fellow eye summarized separately.

Changes in laboratory data will be summarized by cohort.

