#### SE=Study Eye, OU=Both Eyes, XX=two injections

 If there is study drug available at the clinical site, Screening assessments may be conducted on same day as Baseline visit (Day 0), prior to enrollment and intravitreal injection. Informed consent must be obtained before any study related screening activity or treatment is undertaken that is not part of routine care.

 Height and weight measured at Screening only.

 IOP measured using routine practice with a calibrated contact tonometer. For study eyes, IOP will be measured pre and post injection(s).

 Blood samples for PK and PD assessments will be drawn before and 4 hours ±1 hour post injection (for cohort 3, after the second injection).

 At Early Termination, blood samples for PK and PD assessments will be drawn if Day 1 or 1 day post Day 7 treatment PK/PD blood samples were not collected following injection on Day 0 or Day 7.

 For Cohort 3, the study eye receives two study drug injections. The second study drug injection will occur following stabilization of IOP to within 5 mmHg of the pre injection measurement and  $\geq$ 30 minutes after the first injection at the visit.

 The surgical procedure is scheduled independent of this study according to standard of care clinical management of uveal melanoma per patient's treating physician and is not a study procedure.

 Following enucleation, vitreous humor will be collected for ICON-1 and proteomic analysis of TF and other cytokine levels. In addition to the pathology standard procedures of the clinical site, the study-related pathology slides and/or tumor block sample will be prepared and shipped to a central study laboratory for additional evaluations of the tumor (TF expression, ICON-1 binding, immune infiltrate, genetic profiling, and Exome sequencing). Genetic profiling of the tumor previously performed with fine needle aspiration of the tumor does not require repeated testing.

 Ocular assessments for brachytherapy patients only.

 Ocular assessments at early termination visit only if early termination occurs prior to surgical procedure.

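### Causality is recorded against study drug only and TEAEs are tabulated only by cohort, while patients receive 1, 2 or 4 injections, so injection-procedure events can be expected to resemble a dose gradient

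*Combined protocol and SAP*

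**What the plan says.** **Causality.** Section 15.22.4: "The Investigator will assess the relationship of the AE to the study drug as either" related or not related. The list of AE data items in 15.22 has one matching entry: "Relationship to study drug (causality) as determined by the Investigator". Study procedures appear in 15.22.4 only as one factor to weigh ("If the AE is directly related to study procedures or lack of efficacy"), under a lead-in about SAE causality. They are not a recorded category. Elsewhere, relation to a protocol procedure is used only for reporting SAEs that arise before dosing (15.22.6).

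**Injections.** Cohort 1 has one injection on Day 0. Cohort 2 has one on Day 0 and one on Day 7. Cohort 3 has two on each of those days (12.1.2). Appendix B, footnote 6, confirms it: "For Cohort 3, the study eye receives two study drug injections".

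**Analysis.** Occurrence of AEs is a primary endpoint whatever the cause (16.1). Section 17.6: "All adverse events occurring on or after treatment on Day 0 (treatment emergent adverse events, TEAEs) will be summarized by cohort". No table by relationship and no per-injection rate is planned there. Section 17.1 leaves further detail to an SAP whose text is not in the documents reviewed.

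**Prior experience.** Section 8.3 reports that the most frequent events in the 18-patient single-injection study (IT-001) were ocular and "commonly related to the injection procedure or the retinal signs of the underlying AMD". One event, a vitritis, was judged drug-related.

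**The concern.** The primary objective is the tolerability of single and repeated escalating injections, and it will be read from AE tables by cohort. Needle count rises from cohort to cohort with total dose, so an event caused purely by the needle should become more frequent from cohort 1 to cohort 3 even if ICON-1 does nothing.

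The single causality item gives little help in reading such a pattern. A needle-related conjunctival hemorrhage marked related counts against the drug. Marked not related, it is pooled with surgical, tumor and intercurrent events. Either way it stays in the by-cohort TEAE table.

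Two features of the text add to this:

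- Section 15.22.1 sets specific rules for when a post-injection IOP rise is an AE, and writes them for cohort 3 alone. In the other cohorts only the general criterion of clinical significance applies.
- Surgery may follow the last injection by as little as 4 days, and 15.22.1 counts events up to 30 days after the last dose as treatment-emergent. Surgical events therefore enter the same tables, also without an attribution field.

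**Working it through.** **Inputs**

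- Cohort sizes: 2, 3 and 5 planned; 3, 4 and 6 at most (12.4). The maxima sum to 3 + 4 + 6 = 13, which reproduces the total in 17.10. The plan gives no power-based figure to reproduce.
- Dose per injection: 0.3 mg (12.1.2).
- Single-injection study: 18 patients; conjunctival hemorrhage n=5 (8.3).

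**Step 1. Injection count against dose**

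| Cohort | Injections per patient, k | Total dose | Dose per injection | Planned injections |
|---|---|---|---|---|
| 1 | 1 × 1 = 1 | 0.3 mg | 0.3 mg | 2 × 1 = 2 |
| 2 | 2 × 1 = 2 | 0.6 mg | 0.3 mg | 3 × 2 = 6 |
| 3 | 2 × 2 = 4 | 1.2 mg | 0.3 mg | 5 × 4 = 20 |

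Total dose is a fixed multiple of needle count, so by cohort the two are fully collinear.

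**Step 2. Expected gradient with no drug effect**

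The probability that a patient has at least one procedure event is 1 − (1 − p)^k, where p is the risk per injection. The illustrative value is p = 5/18 = 27.8%, with exact 95% interval 9.7% to 53.5%. It assumes that n=5 counts patients, that all five events were due to the procedure, and that injections are independent. The other values of p are assumptions that show the range.

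| Assumption | Cohort 1 | Cohort 2 | Cohort 3 |
|---|---|---|---|
| p = 5/18, per injection (k = 1, 2, 4) | 27.8% | 47.8% | 72.8% |
| p = 9.7% (lower limit) | 9.7% | 18.4% | 33.5% |
| p = 53.5% (upper limit) | 53.5% | 78.4% | 95.3% |
| p = 10% | 10.0% | 19.0% | 34.4% |
| p = 5% | 5.0% | 9.8% | 18.5% |
| p = 5/18, per injection day (k = 1, 2, 2) | 27.8% | 47.8% | 47.8% |

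For example, in cohort 3 at p = 5/18: 1 − (13/18)^4 = 72.8%.

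**Step 3. Would these small cohorts show it?**

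Exact binomial enumeration over both sets of cohort sizes (2/3/5 and 3/4/6) gives the chance that cohort 3 shows a higher observed proportion than cohort 1:

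- Risk per injection: 87% at p = 5/18, 75% at 10%, 58–62% at 5%.
- Risk per injection day: 65–69% at p = 5/18, 54% at 10%, 36–40% at 5%.

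With risk per injection and p from 5% to 5/18, the chance that proportions never fall from one cohort to the next and cohort 3 ends above cohort 1 is about 48–55%.

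**Step 4. What a per-injection rate would show**

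For a pure needle event at p = 5/18 with risk per injection, expected events per patient are 1 × 0.278 = 0.28, 2 × 0.278 = 0.56 and 4 × 0.278 = 1.11. Dividing by k returns 27.8% in every cohort, so the gradient disappears on that scale.

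**The case against.** **Objections that stand**

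- The causality item is not the sole cause. The TEAE table in 17.6 is not split by relationship, so the gradient would appear there under any causality scale. A new field helps only if the tables use it.
- A reader might infer that the data cannot be separated afterwards. The documents do not support that. Event description and dates (15.22), date and time of each treatment (12.5), per-patient dosing listings (17.5) and separate study-eye and fellow-eye tables (17.6) allow partial sorting among at most 13 patients, and a per-injection rate needs no new field. What is lost is the investigator's attribution made at the time.
- A reader might infer that the tables will show a dose effect. Step 3 shows only that this is likely under some assumptions.
- A reader might infer that escalation decisions would be distorted by the events used here. Conjunctival hemorrhage is not in the DLT definition of 12.4, so the illustration does not bear on escalation.
- A reader might infer that IT-001 had a procedure-causality field. Section 8.3 does not describe its form; the remark may be a clinical reading of listings.
- The burden of four injections is itself part of the primary question, so counting procedure events by cohort is legitimate. The gap is that they are not also shown apart.

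**Objections that do not defeat the point**

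- Investigators may weigh study procedures and mark an event not related. That removes it from the drug's count but does not identify it as a needle event.
- An SAP could add tables or per-injection rates, but cannot tabulate an attribution that the eCRF never collected.

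**Conclusion.** The point holds in a limited form. With one drug-only causality item, TEAE tables by cohort alone, and needle count collinear with total dose, procedure events are expected to look like a dose gradient in the primary safety tables. The illustrative size is 28%, 48% and 73% of patients with no drug effect; 10%, 19% and 34% at a 10% risk per injection; and 28%, 48% and 48% if risk acts per injection day, when the step from cohort 2 to cohort 3 vanishes.

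These figures rest on the assumptions in step 2 and on carrying a rate from wet AMD to uveal melanoma. The documents do not say how many of the five hemorrhages were due to the procedure. The gradient may not appear in cohorts this small, and no inferential testing is planned (17.1). This is an inexpensive improvement to how the primary safety data will be read, not a flaw that invalidates the study.

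**What to change.** - **15.22, 15.22.4 and the AE eCRF:** record related or not related separately for (a) ICON-1, (b) the intravitreal injection procedure and (c) the enucleation or plaque procedure.
- **17.6:** tabulate study-eye TEAEs by cohort for each attribution, and give injection-procedure events also per injection.
- **17.6, one added sentence:** with no sham or vehicle injection, this reduces but does not remove the confounding of injection count with dose.

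The cost is two yes/no fields, one extra table and two more open-label judgements per AE, which are opinions and not a control. The fields need to be in place before AE data are entered, because attribution made at the time cannot be recovered later. No dose, schedule or clinical rule changes.

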#### 15.22.5 Adverse Events of Special Interest (AESIs)

AESIs are events of medical and scientific concern specific to the investigational product, for which ongoing monitoring and rapid communications by the investigator to the sponsor and Safety Review Committee is appropriate. Ocular adverse events that qualify as an AESI (even if non-serious) include the following:

- Ocular inflammatory event of CTCAE Grade  $\geq 3$
- Vitreous or retinal hemorrhage event interfering with visualization of the tumor or retina of CTCAE Grade  $\geq 2$
- Any acute onset treatment-emergent vision-threatening condition as assessed by the investigator

## **15.22.6 Adverse Event Reporting Procedures**

The occurrence of AEs should be sought by non-direct questioning of the subject at each scheduled or unscheduled study visit. At each visit, study personnel should ask the following question: "Have you had any problems since your last visit?" AEs may also be detected when they are volunteered by the subject during and between visits or through physical examination, or other assessments. All AEs (serious and non-serious) reported by the subject will be reviewed by a qualified physician participating in the study and must be recorded on the subject's source documents and AE eCRF.

An AE that is classified as "serious" requires expeditious handling and reporting to the Sponsor or designee within 24 hours of site notification to comply with regulatory requirements.

All SAEs and AESIs, whether or not related to study drug, must be reported immediately to the Sponsor or designee by entering the SAE/AESI information directly into the electronic data capture (EDC) system (AE eCRF) within 24 hours after the Investigator becomes aware of the event.

Note that any SAEs that occur after the subject has provided written informed consent but before administration of study drug and are considered related to a protocol procedure must also be reported to the Sponsor or designee within 24 hours after the Investigator's awareness of the event.

Investigators should not wait to receive additional information to fully document an SAE before reporting the event to the Sponsor or designee. If only limited information is initially available, follow-up information regarding the SAE is required. Additional relevant information such as hospital records, laboratory test results, discharge summaries and/or autopsy reports should be provided as soon as these are available. These SAE follow-up documents should be uploaded into the EDC system for informational purposes; however, if a document cannot be uploaded, it should be submitted to Iconic Therapeutics Drug Safety:

## 15.22.7 Reporting Serious Adverse Events to Regulatory Agencies

An AE, whether serious or non-serious, is considered "unexpected" if the event is not reported in the clinical safety section of the reference document (e.g., Investigator Brochure or Package Insert) or if the event is of greater severity or frequency than is reported in the reference document.

Expedited SAE reports are those SAEs that are both unexpected based on the reference document and considered related to the study drug (i.e., the relationship cannot be ruled out). The Sponsor will determine which SAEs qualify for expedited reporting.

Reports of those SAEs that qualify for expedited reporting submitted to regulatory agencies in accordance with applicable local regulation (e.g., 21 Code of Federal Regulations [CFR] 312.32 and, as applicable, European Union Directive 2001/83/EC and 2001/20/EC).

Expedited reports will be also distributed to Investigators. Upon receiving such notices, the Investigator must review and retain the notice with the Investigator Brochure and immediately submit a copy of this information to the governing IRB/IEC in accordance with institutional guidelines and local regulations.

## 15.22.8 Pregnancy

Pregnancy alone is not an AE. However, any report of pregnancy that occurs in a female subject within 30 days after the subject's last administration of study drug, and that becomes known to the Investigator, must be reported to the Sponsor even if the subject is withdrawn from study.

If a subject or Investigator suspects that a subject may be pregnant prior to study drug administration, the study drug administration must be withheld until the results of blood serum pregnancy tests are available. If pregnancy is confirmed, the subject must not receive the study drug and must not be enrolled in the study. If pregnancy is suspected while the subject is receiving study treatment, the study drug must be withheld immediately until the result of a pregnancy testing is known. If pregnancy is confirmed, the study drug will be permanently discontinued and the subject withdrawn from the study. The Investigator must follow the pregnancy to conclusion, and collect data on both maternal and fetal outcome including followup information regarding the course of the pregnancy and perinatal and neonatal outcomes.

A Pregnancy Report form will be submitted to the Sponsor, at a minimum, initially and at the end of the pregnancy. The Investigator is also encouraged to submit to the Sponsor trimester follow up reports during the pregnancy. The outcome of the pregnancy and any complications occurring during the pregnancy or the delivery must be reported to the Sponsor.

A miscarriage or spontaneous abortion will be considered an SAE, and will be reported to the Sponsor according to the procedure described in Section 15.22.5.

